1.3. Evaluation Period and Evaluation Range

The following formula is used to calculate the number of days.

Number of days = [Observation Day] - [Start Day of Administration] + 1 (The same day is considered as the first day)

Furthermore, the pre-administration value adopts the "start date of administration". However, if there is no data for the "start date of administration", the data closest to the start date of administration will be adopted. This pre-administration value is used as the baseline.

The "clinical test values" and "progression of renal function, etc." will adopt the data from the final volume and final SEQ if there is the same date among the data with test values.

Evaluation Period	Standard Number of Days	Permissible Range
Pre-administration	One day before the start of	Within 0 days
	administration	
Start date of administration	Start date of administration	Day 1

1.4. Matters Concerning Statistical Analysis Output

1.4.1. Summary Statistics

Calculate the mean, standard deviation, minimum value, median, and maximum value.

1.4.2. Significance Level and Confidence Interval of the Test

The significance level of the test is set at a two-tailed 5%, and the confidence level of the confidence interval is set at a two-tailed 95%.

1.4.3. Display Digits

The display digits (valid digits) for each clinical test value item shall be as per the table below.

Classification	Item Name	Unit	Display Digits*
Transition of Kidney volume	Total Kidny Volume of Both Sides	mL	0.001
Transition of Renal	Height	cm	0.1
Function, etc.	Weight	kg	0.01
	Serum Creatinine Value	mg/dL	0.01

	e-GFR	mL/min/1.73m ²	0.001
	Creatinine Clearance	mL/min	0.1
Hematological Biochemical Examination	AST(GOT)	IU/L	0.1
	ALT(GPT)	IU/L	0.1

^{*} The number of digits displayed after rounding off.

1.4.3.1. Minimum Value, Maximum Value

Display up to the significant digits of the data.

1.4.3.2. Ratio, Percentage

Round to the second decimal place and display up to the first decimal place. However, in the case of the incidence rate of side effects, round to the third decimal place and display up to the second decimal place.

1.4.3.3. p Value

Round to the fourth decimal place and display up to the third decimal place. However, if the p-value is <0.001, display it as p<0.001.

1.4.4. Software

The following software will be used for analysis:

- SAS 9.4 or later
- Microsoft Excel 2016 or later

1.4.5. Sample Code

1.4.5.1. Estimation of cumulative incidence over time using the Kaplan-Meier method and creation of a dataset for graphing.

```
proc lifetest data =[input dataset] alpha = 0.05 method = KM plots = (s, lls) outs = [output dataset1];
    strata [strata variable] ;
    time [time variable] * [censoring variable] (0) ;
run;
proc means data = [output dataset1] max noprint;
    class [strata variable];
    var SURVIVAL;
    output out = [output dataset2] min = [min output variable];
run;
data [output dataset2];
    set [output dataset2];
    if [strata variable] ^= .;
run;
```

```
data [output dataset1];
   merge [output dataset1] [output dataset2];
   by [strata variable];
   if SURVIVAL = . then SURVIVAL = [min output variable];
run;
data [graph output dataset];
   set [output dataset1];
   [rate output variable] = 1 - SURVIVAL;
   output;
   if _CENSOR_ = 1 then do;
      [rate output variable] = [rate output variable] + 0.025;
     output;
     [rate output variable] = [rate output variable] -0.025;
     output;
   end;
run;
```

1.4.5.2. Linear Mixed Effects Model

run ;

Note: [pre-post treatment group variable] and [case number variable] are categorical values, [time (year) variable] is a continuous value.

The INT in the random statement is specified as is, meaning the intercept. The intercept and slope vary between individuals.random.

2. Statistical Analysis

2.1. Case Composition

2.1.1. Excluded Cases

A list of case numbers and reasons for exclusion will be created for cases excluded from safety analysis and efficacy analysis.

2.2. Patient Background Factors and Treatment Factors

[Analysis Target]

The target for the safety analysis will be aggregated.

[Analysis Method]

For each item of patient background factors and treatment factors shown in Table 1, the number of cases and composition ratio will be calculated by category. Summary statistics will be calculated for continuous variables (Age, e-GFR (pre-administration), creatinine clearance (pre-administration), total kidney volume on both sides (pre-administration)).

For patient background factors, the information described in the final volume of CRF will be adopted as a rule, and the first volume will be adopted depending on the item. For treatment factors and clinical test values, the information described in all collected volumes will be adopted.

The pre-dose creatinine clearance (Ccr) is calculated using the pre-dose serum creatinine value for cases with pre-dose values, using the following formula¹:

- For men: $Ccr = \{(140\text{-age}) \text{ x weight(kg)}\} / \{72 \text{ x serum creatinine value(mg/dL)}\}$
- For women: $Ccr = \{(140\text{-age}) \text{ x weight(kg)}\} / \{72 \text{ x serum creatinine value(mg/dL)}\} \times 0.85$

The pre-dose e-GFR is prioritized according to the physician's notation. If there is no physician's notation, it is calculated for cases with pre-dose values using the following formula²:

- For men: e-GFR = $(194 \text{ x serum creatinine value} (\text{mg/dL})^-1.094 \text{ x age}^-0.287)$
- For women: e-GFR = $(194 \text{ x serum creatinine value} (\text{mg/dL})^-1.094 \text{ x age}^-0.287) \text{ x } 0.739$

The height-corrected total kidney volume on both sides is calculated using the following formula:

• Total kidney volume on both sides (mL) ÷ (height(cm) ÷ 100)

Table 1. Distribution of Cases by Patient Background Factors and Treatment Factors

Item Name	Category	Aggregation Method
	1. Male	Frequency Tabulation
Gender	2. Female	Final Subdivision Adoption of
	3. Unknown	CRF
		Summary statistics,
		Frequency tabulation
	1. Under 15 years old	Adopt the date of birth from the
	2. 15 years old and above but under 65	final volume of the CRF, and
Age	3. 65 years old and above	calculate the age from the start
	4. Unknown	date of this drug administration.
		If the date of birth in the final
		volume of the CRF is blank or
		non-existent, adopt the age from

Item Name	Category	Aggregation Method
		the first volume of the CRF.
	1. Less than 15	Summary statistics, Frequency
	2. 15 to less than 30	tabulation
e-GFR (Before	3. 30 to less than 45	Full volume adoption
Administration)	4. 45 to less than 60	Prioritize physician's notes,
$(mL/min/1.73m^2)$	5. 60 to less than 90	calculate if there are no
	6. 90 and above	physician's notes.
	7. Unknown	
Bilateral Total Kidney	1. Less than 750	Summary statistics, Frequency
Volume (Pre-	2. 750 to less than 1500	tabulation
administration)(mL)	3. 1500 to less than 3000	Full volume adoption
* Cases with data up to 3	4. 3000 to less than 4500	
months (92 days) before	5. 4500 to less than 6000	
the administration of	6. 6000 and above	
Samusca.	7. Unknown	

2.3. Safety-related Aggregation

- 2.3.1. Manifestation Status of ADRs and Infectious Diseases
- 2.3.1.1. Manifestation status of adverse events, ADRs, and infectious diseases in post-marketing surveilances, etc., and manifestation status of ADRs and infectious diseases in additional drug safety monitoring plans

[Analysis Target]

Safety analysis target cases

[Analysis Method]

As shown in Table 2, the number of safety analysis target cases and the number of cases of adverse events, etc., are aggregated for the usage performance survey, and the manifestation rate of adverse events, etc., is calculated. In addition, frequency aggregation is performed separately for SOC and PT, and the manifestation rate is calculated.

Table 2. Overview of the manifestation of ADRs and infectious diseases

Item Name	Definition content
Causal Relationship	Adopt the causality determined by the physician.
Severity	Adopt the severity determined by the physician.
Case Number	The case numbers used to count the number of survey cases and the number of cases with ADRs, etc., are as follows: ADPKD: Patient-specific number (BaseEntryNO)
Number of Cases Subject to Safety Analysis	Aggregate the number of cases for safety analysis.
Number of Cases with ADRs, etc.	If multiple ADRs occur in the same case, count it as one case.
Incidence Rate of ADRs, etc.	Number of cases with ADRs / Number of cases for safety analysis x 100
Major Classification by Organ	MedDRA SOC (name)
Basic or Subordinate Terms	MedDRA PT (name)

^{*}Display order: SOC international agreement order, PT code ascending order

	Item Name	Definition content
Incidence Rate by SOC, PT		SOC: Number of cases with ADRs / Number of cases for safety analysis x 100 PT: Number of cases with ADRs / Number of cases for safety analysis x 100
ADPKD	Usage Performance Survey (Post-Marketing Cases)	Target all cases for safety analysis.
Examination	on Item Name1	Name assigned from safety review items.
Examination Item Name2		Name assigned from safety review items. If there is a name different from the examination item name 1, output it.

2.3.2. List of serious adverse events in post-marketing surveillance, List of serious ADRs in post-marketing surveillance

[Analysis Target]

Safety analysis target cases

[Analysis Method]

As shown in Table 3, for the post-marketing surveillance, the number of survey cases and the number of cases with serious adverse events are aggregated, and the incidence rate of serious adverse events is calculated. In addition, frequency aggregation by SOC and PT is performed, and the incidence rate is calculated. In the PT-specific aggregation, events where the causal relationship has been denied (unrelated) are also aggregated, but if there are events that are related and events where the causal relationship has been denied in the same PT in the same case, the related events are prioritized and not counted as events where the causal relationship has been denied.

In addition, similar aggregation is performed for serious ADRs, but aggregation of events where the causal relationship has been denied is not performed in the PT-specific aggregation.

Table 3. Overview of the Occurrence Status of Serious Adverse Events

Item Name	Definition content
Severity	Adopt the severity determined by the physician.
Causal Relationship	Adopt the causality determined by the physician.
Case Number	The case numbers used to count the number of survey cases and the number of cases with ADRs, etc., are as follows: ADPKD: Patient-specific number (BaseEntryNO)
Number of Cases investigated	Aggregate the number of cases for safety analysis.
Number of cases with adverse event occurrence	If multiple serious adverse events occur in the same case, it is counted as one case.
Incidence Rate of adverse event, etc.	Number of cases with adverse event occurrence / Number of cases subject to safety analysis x 100
Major Classification by Organ	MedDRA SOC (name)
Basic or Subordinate Terms	MedDRA PT (name)

^{*}Display order: SOC international agreement order, PT code ascending order

Item Name		Definition content
Incidence Rate by SOC, PT		SOC: Number of cases with ADRs / Number of cases for safety analysis x 100 PT: Number of cases with ADRs / Number of cases for safety analysis x 100
ADPKD	Usage Performance Survey (Post-Marketing Cases)	Target all cases for safety analysis.
Examination Item Name1		Name assigned from safety review items.
Examination Item Name2		Name assigned from safety review items. If there is a name different from the examination item name 1, output it.

2.3.2.1. Duration until ALT and AST exceed the upper limit of the reference value

[Analysis Target]

Cases where ALT has increased from before administration and are subject to safety analysis, or cases where AST has increased from before administration and are subject to safety analysis.

[Analysis Method]

The number of days elapsed from the start date of administration of this drug until the day when ALT or AST first became 3 times or more of the upper limit of the reference value is estimated by the Kaplan-Meier estimation method, and the cumulative exceedance rate is plotted. The termination date is the end date of administration of this drug. It also shows the At Risk (risk set) at the time.

The upper limit of the reference value is 30U/L for ALT and 30U/L for AST.

2.4. Aggregation Regarding Efficacy

2.4.1. Rate of Change in Bilateral Total Kidney volume

[Analysis Target]

Cases subject to efficacy analysis

Cases with one measurement date at baseline and before baseline are classified as the pre-administration group, and cases with one or more measurement dates during administration are classified as the post-administration group.

An analysis will be conducted on cases that fall into either the pre-administration group or the post-administration group.

[Analysis Method]

Regarding the rate of kidney volume increase

1) To reduce heterogeneity of variance and achieve linearity over time, the data of bilateral total kidney volume is log-transformed (log10). This log-transformed bilateral total kidney volume is set as the dependent variable, and a linear mixed-effects model is fitted as repeated measures data. The explanatory variables of the model are the administration group, time (years), patient, interaction of administration group and time, and interaction of patient and time as fixed effects, and the intercept and slope of the time axis for each patient as random effects. The variance-covariance matrix of the random effects is unstructured. The annual change rate and 95% confidence interval are returned to

their original scale by (10 estimated value -1) x 100.

Time (years) is calculated as "(measurement date - baseline +1) \div 365.25".

- 2) The pre-administration group calculates the rate of kidney volume change from before the baseline to the baseline, and the post-administration group calculates the rate of kidney volume change from the baseline to after the baseline. The rate of change in kidney volume is calculated using the following formula.
 - Rate of kidney volume change = {((post-administration value pre-administration value) / pre-administration value) x 100} / "period (years) from the start of administration of this drug to the measurement date"

Also, the Estimated Slope and Estimated SE are calculated for each of the pre-administration group and the post-administration group, and a graph is created. The difference in the Estimated Slope between the pre-administration group and the post-administration group and its test result are displayed as the estimated value of the parameter based on the solution of the fixed effect of the administration group and time and the p-value based on the t-distribution.

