Cases excluded from efficacy analysis	Among the cases subject to safety analysis, cases that fall under the following items. 1) Cases where the purpose of use is not "suppression of ADPK progression with a rapid kidney volume increase in patients with increase kidney volume" 2) Cases where the efficacy evaluation items have not been measured after the administration of the drug, or there is no efficacy data measured with the allowable range at each evaluation time	
Cases subject to efficacy analysis	Among the cases subject to safety analysis, cases excluding those excluded from the efficacy analysis.	

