2.4.2. Change in e-GFR

[Analysis Target]

Cases subject to efficacy analysis

Cases with one measurement date at baseline and before baseline are classified as the pre-administration group, and cases with one or more measurement dates during administration are classified as the post-administration group.

Analyses targeting cases that apply to either the pre-administration group or the post-administration group (however, excluding cases that only have two points: one at baseline and one either before baseline or during administration) will be conducted.

[Analysis Method]

- 1) e-GFR will be treated as the dependent variable using actual values, and a linear mixed-effects model will be applied as repeated measurement data. The explanatory variables of the model are the administration group, time (years), patient, interaction of administration group and time, and interaction of patient and time as fixed effects, and the intercept and slope of the straight line over time for each patient as random effects. The variance-covariance matrix of the random effects will be unstructured.
- 2) The change in e-GFR from before baseline to baseline for the pre-administration group, and the change in e-GFR from baseline to after baseline for the post-administration group will be calculated. The change in e-GFR will be calculated using the following formulas:
 - Pre-administration change = (Pre-baseline value Baseline)
 - Post-administration change = (Post-administration value Baseline)

In addition, the Estimated Slope and Estimated SE will be calculated separately for the preadministration group and the post-administration group. The difference in the Estimated Slope between the pre-administration group and the post-administration group and its test result will be displayed as the estimated parameter values based on the solution of the fixed effects of the administration group and time, and the p-value based on the t-distribution.

Reference

- 1. Marc Froissart, Jerome Rossert, Christian Jacquot, Michel Paillard and Pascal Houillier: Predictive performance of the modification of diet in renal disease and Cockcroft-Gault equations for estimating renal function. J Am Soc Nephrol 16: 763-73, 2005.

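### The pre/post comparison pools patients in either group, so item 2) compares different sets of patients, and the tested slope difference may be partly between patients, depending on how patient-by-time is fitted

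*SAP*

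**What the plan says.** SAP 2.4.1 (kidney volume) forms two groups. For the comparator: "Cases with one measurement date at baseline and before baseline are classified as the pre-administration group". For the treated period: "cases with one or more measurement dates during administration are classified as the post-administration group". The second definition asks for no earlier value. The analysis set is the union: "An analysis will be conducted on cases that fall into either the pre-administration group or the post-administration group".

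SAP 2.4.2 (e-GFR) uses the same union, "Analyses targeting cases that apply to either the pre-administration group or the post-administration group", and removes only the sparsest cases: "excluding cases that only have two points: one at baseline and one either before baseline or during administration". A one-sided case with more points stays in.

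SAP 1.2 drops from the efficacy set "Cases where the efficacy evaluation items have not been measured after the administration of the drug". Most one-sided cases are therefore post-only.

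Item 1) in both sections is the mixed model that supplies the tested slope difference. Its fixed part includes "interaction of administration group and time, and interaction of patient and time as fixed effects", and the same sentence adds "the intercept and slope of the time axis for each patient as random effects". The note in 1.4.5.2 says that intercept and slope vary between individuals. Item 2) calculates changes separately for each group and specifies no test. Neither section describes an analysis restricted to patients who are in both groups.

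**The concern.** The SAP describes no control arm. This before/after contrast, tested at a two-sided 5% level (SAP 1.4.2), is its only efficacy comparison. It reads most naturally as the same patients before and on drug, and the union set does not deliver that. The protocol starts observation at the first dose, so an earlier kidney volume is history that only some patients will have. The indication is for rapid volume increase, so it is plausible, though not shown, that patients measured earlier are those already known to be growing fast. If so, the comparator is steeper than the population behind the treated slope, and the treated period looks better even if the drug does nothing.

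**Working it through.** The documents give no effect size, SD, power or expected overlap for this comparison, so there is no planned figure to reproduce. The mechanism was checked with the drug effect set to zero.

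**Assumptions (none from the documents).** Share p of patients with a pre-baseline value; true growth s1 in them and s0 = 4%/yr in the rest; every patient has on-drug values.

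**Item 2), crude group means.** The pre mean is s1. The post mean is p·s1 + (1−p)·s0. The false difference is −(1−p)(s1 − s0).

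- p = 0.4, s1 = 6, s0 = 4: post = 0.4×6 + 0.6×4 = 4.8, and 4.8 − 6.0 = −1.2 points/yr.
- p from 0.3 to 0.9 and a gap of 1 to 3 points: from −(0.1)(1) = −0.1 to −(0.7)(3) = −2.1 points/yr.

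**Item 1), random intercept and slope.** This is the exact expected generalised-least-squares group-by-time estimate, back-transformed as in 2.4.1. Further assumptions: one pre value 0.5 to 2 years before baseline, baseline counted in both periods, roughly yearly on-drug values, intercept SD 0.25 and residual SD 0.02 (log10), slope SD about 4%/yr, variances known, gap 2 points. False difference in points/yr:

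| p | crude | 1 on-drug value | 3 values | 5 values |
|---|---|---|---|---|
| 0.3 | −1.4 | −0.96 | −0.28 | −0.09 |
| 0.4 | −1.2 | −0.83 | −0.24 | −0.08 |
| 0.5 | −1.0 | −0.68 | −0.20 | −0.07 |
| 0.7 | −0.6 | −0.41 | −0.12 | −0.04 |
| 0.9 | −0.2 | −0.14 | −0.04 | −0.01 |

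Varying the residual SD over 0.01 to 0.04 and the slope SD over 2 to 4%/yr, at p = 0.5 with three on-drug values, gives −0.06 to −0.74. Across the same SDs at p = 0.4, with one to five on-drug values, the model's pre slope is about 4.8 to 6.0%/yr, although the true value in those patients is 6.0.

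**Item 1), patient-by-time fixed.** In a post-only patient the group indicator is always 1, so group-by-time equals time and is absorbed by that patient's own slope. Such patients add nothing. In one simulated set of 400 patients, 200 of them with both periods, the group-by-time estimate was −0.00069 log10/yr from all 400 and −0.00069 from the 200. The fixed part is over-parameterised: 4 + 400 + 400 = 804 columns, rank 802.

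**Restricting to both periods.** The same patients then supply both slopes, so the between-patient part is zero. With the random-slope model and p = 0.4, the expected slopes are 6.0 and 6.0. The SE of the difference rises by up to about 4% with three on-drug values, or about 15% if the two lines are forced to meet at baseline. With one on-drug value it rises by roughly 10 to 30%.

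**The case against.** Several points against the concern stand.

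- A reader might infer that the tested difference is, as a matter of fact, partly between different patients. The documents do not support that. On the literal fixed patient-by-time wording it is wholly within-patient. The note in 1.4.5.2 points towards random slopes, but the model code is not legible in the text available for this review, so it cannot settle the matter.
- The −1.2 belongs to item 2), for which no test is specified. Under random slopes the model shrinks the between-patient part, and with several on-drug values it is usually small.
- Nothing in the documents says that patients with earlier measurements grow faster. The efficacy set excludes uses outside the rapid-growth indication, so every case is nominally a rapid grower.
- The pre group is not strictly nested in the post group. A case whose only post-dose efficacy value is e-GFR could be pre-only for kidney volume.
- For e-GFR, the two-point exclusion already removes the one-sided cases most exposed to the problem. The concern is smaller there, and no e-GFR magnitude has been calculated.
- Using all available data in a mixed model is legitimate. Restricting to both periods still leaves a comparator drawn from patients with earlier values.

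Two things remain. No model term protects the item 2) figures. And the SAP lists patient terms as both fixed and random, so it does not secure the reading under which the test is safe. Even under that reading, the tested difference rests only on patients with both periods, which the stated N would not show.

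**Conclusion.** The concern holds in limited form. It is certain that the analysis set is a union, that the pre slope rests only on patients with a pre-baseline value, and that the item 2) per-group figures describe different sets of patients. It is conditional that the tested slope difference carries a between-patient part: yes with random patient slopes, no with fixed patient-by-time. Direction and size are assumptions. Under the values tried, the false difference in item 2) runs from −0.1 to −2.1 points/yr. In the random-slope model with a 2-point gap, residual SD 0.02 and slope SD about 4%/yr, it runs from about −0.01 to −0.96, depending mainly on the number of on-drug values and the overlap. It would be wrong to conclude that the result is biased in favour of the drug; the documents only leave that possible and give no means to judge it. This is a cheap improvement, not a reason to discard the analysis.

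**What to change.** In SAP 2.4.1 and 2.4.2:

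1. Pre-specify the slope difference, the displayed slopes and the item 2) summaries in cases with both a pre-baseline and an on-drug value. Make this the before/after contrast, or at least a named sensitivity analysis beside the either-group result.
2. Report the number in each group and the overlap, with baseline age, e-GFR and kidney volume for cases with and without a pre-baseline value.
3. State one model by removing the duplicated patient terms, fixed or random, and make the sample code in 1.4.5.2 agree.

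The cost is SAP wording and a rerun on data already collected. The downside is a smaller N and a narrower population. The loss of precision is modest when patients have several on-drug values and larger (roughly 10 to 30% in SE under the assumptions tried) when they have only one. The restriction removes the between-patient part of the contrast; it does not make patients with earlier measurements representative of the rest.

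### SAP 2.4.1 and 2.4.2 enter each patient's intercept and slope as both fixed and random effects, so the group-slope SEs and the annual-change CI cannot be estimated from the data as worded

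*SAP*

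**What the plan says.** SAP 2.4.1, Analysis Method 1), models log10 bilateral total kidney volume. Its fixed effects are administration group, time, patient and group by time, followed by "interaction of patient and time as fixed effects, and the intercept and slope of the time axis for each patient as random effects". It adds: "The variance-covariance matrix of the random effects is unstructured". SAP 2.4.2, Analysis Method 1), uses the same structure for e-GFR: "interaction of patient and time as fixed effects, and the intercept and slope of the straight line over time for each patient" as random effects, and "The variance-covariance matrix of the random effects will be unstructured".

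Three outputs depend on these models.
- **Group slopes.** In 2.4.1, "the Estimated Slope and Estimated SE are calculated for each of the pre-administration group and the post-administration group"; 2.4.2 asks for the same for e-GFR.
- **Annual change (2.4.1 only).** "The annual change rate and 95% confidence interval are returned to" the original scale.
- **Slope difference.** Both sections report the pre/post difference with a t-based p-value.

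On eligibility, 2.4.1 says "cases with one or more measurement dates during administration are classified as the post-administration group".

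Of the sample code in 1.4.5.2, the available text holds only the end and a note. The note explains that the RANDOM statement carries an intercept and that patients differ in both intercept and slope. The MODEL statement is not visible, which is not itself a fault.

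**The concern.** A fixed patient effect and a fixed patient-by-time effect give every patient a free intercept and slope. A random intercept and slope per patient describe the same quantities again. Once the fixed part has absorbed them, nothing is left from which to estimate the random covariance, although the SEs of the average slopes depend on it.

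Kidney volume and e-GFR are the only efficacy items in the protocol's list of items to be analyzed. A programmer who follows the prose gets SEs and a CI set by how the software handles an unidentified covariance. One who fits an ordinary random-coefficient model gets different ones.

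**Working it through.** The plan gives no variances and no figure to reproduce. Steps 1 to 3 need no assumed variance for their conclusions; steps 4 to 6 are illustrations on assumed inputs.

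**1. Rank.** Take 20 patients: 10 with annual records from year −2 to 3 and 10 with records from year 0 to 3, so 10×6 + 10×4 = 100 records. X is the fixed design and Z holds the per-patient intercept and slope columns.

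| Model | rank(X) | rank([X Z]) |
|---|---|---|
| As worded | 42 | 42 |
| Without patient and patient × time | 4 | 42 |

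As worded, X has 2×20 patient columns plus group and group × time. Z adds nothing to it.

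**2. Likelihood.** REML log-likelihood in one simulated data set, residual variance 0.0004, at four covariance matrices G of the random effects:

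| G | As worded | Two terms removed |
|---|---|---|
| 0 | 150.269 | −3669.1 |
| diag(0.04, 0.000144) | 150.269 | 174.6 |
| [[0.5, 0.01], [0.01, 0.01]] | 150.269 | 129.1 |
| [[5, 0.1], [0.1, 1]] | 150.269 | 64.1 |

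REML carries no information on G. The SAP names neither REML nor ML. In a separate 150-patient data set, −2ML was −4159.0 near G = 0, −3081.2 at the true G and −2741.4 at 4G, so ML pushes G to zero.

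**3. Single-record patients.** Cut one patient without pre-treatment records to a single on-treatment record. As worded, rank(X) is 41, and it becomes 42 when the contrast for the mean of the patient slopes is added, so that group slope is not estimable. Adding the slope-difference contrast leaves the rank at 41, so the difference is still estimable. With the two terms removed, the group slope is estimable (4 and 4).

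**4. Size of the SE error.** Assumed: 200 patients, 100 with both periods and 100 with baseline and later records only; annual records as in step 1; slope SD τ = 0.012 log10 per year; residual SD 0.02. The group slope is taken as the mean of the patient slopes with the common group shift. Section 2.4.1 runs the pre period up to baseline and also says "the post-administration group calculates the rate of kidney volume change from the baseline to after the baseline", so two layouts are shown. A puts the baseline record in the post group. B puts it in the pre group for patients with both periods.

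Variance of a group slope = (residual term) + τ²/N. The sum of squares of post times is 5 for years 0–3 and 2 for years 1–3.

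- A, τ = 0: 0.02/√(5×200) = 0.00063.
- A, τ = 0.012: √(0.012²/200 + 0.0000004) = 0.00106.
- B, τ = 0: √[0.0004×(100/2 + 100/5)/200²] = 0.00084.
- B, τ = 0.012: √(0.00000072 + 0.0000007) = 0.00119.

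At τ = 0.05 the same formula gives 0.00359 (A) and 0.00363 (B). Relative to the correct SE, the zero-covariance SE is 0.60 (A) or 0.70 (B), and the SE at 0.05 is about three times too large.

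Coverage at zero covariance = 2Φ(1.96 × SE at zero / correct SE) − 1:

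| Setting | Post | Pre |
|---|---|---|
| A | 76% | 94% |
| B | 83% | 92% |
| B, all patients with both periods | 86.5% | 86.5% |
| A, baseline plus one later record only | 93% | – |
| e-GFR, assumed slope SD 2.5, residual SD 4 mL/min/1.73m²: A | 75% | – |
| e-GFR, same SDs: B | 82% | – |

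**5. Effect on the annual-change CI.** Layout A, assumed growth of 4.7% per year, SE scaled by √(200/N):

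| N | Zero covariance | Correct | Slope SD 0.05 |
|---|---|---|---|
| 200 | 4.40–5.00 | 4.20–5.20 | 3.02–6.41 |
| 800 | 4.55–4.85 | 4.45–4.95 | 3.85–5.55 |
| 1,600 | 4.59–4.81 | 4.52–4.88 | 4.10–5.30 |

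The protocol plans 1,600 patients, with at least 800 on long-term treatment. How many will have usable kidney volumes is not known.

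**6. Slope difference.** Its SE is the same at every covariance: 0.00297 (A) and 0.00200 (B). Its efficiency against the ordinary random-coefficient model is 98% (A) and 82% (B).

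**The case against.** **The code may already be right.** What survives of 1.4.5.2 fits an ordinary random-coefficient model. If the MODEL statement has that form, reported results do not change and the fault is prose that contradicts the code. This stands as a limit. It does not rescue the prose, which makes the same error in two sections.

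**Under ML the covariance is not arbitrary.** True: it goes to zero. That is the case in which the SEs are too small. The too-large case applies only where the software returns some other value under REML, and no procedure has been shown to return 0.05.

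**The only test in these sections is untouched.** True when patients share a common slope change: the SE of the difference does not depend on the covariance. What is affected is the group-slope SEs and one CI.

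**The coverage figures depend on assumptions.** True. With baseline and one later record, post coverage is 93%, and at 800 or more patients the error in each limit is small. Too small also means relative to a wider population of patients, which is the inference that random effects imply.

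**The single-record case may not occur.** 2.4.1 and 2.4.2 elsewhere seem to presume a baseline record. But the eligibility wording in 2.4.1 admits such a patient, and one is enough. The point remains conditional.

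**Conclusion.** The concern holds: as worded, both models are over-specified and the unstructured covariance cannot be estimated. That conclusion is exact and rests on no assumed variance. The SEs of the pre and post slopes in both sections, and the annual-change CI in 2.4.1, then depend on a value the data do not determine.

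The size is illustrative. On the assumed inputs the post-slope SE at zero covariance is 0.60 to 0.70 of the correct one, but the resulting error is about 0.1 percentage point per CI limit or less at 800 or more patients. The pre/post slope-difference test is not invalidated; it loses some efficiency. This should be fixed, with medium confidence about the effect on results because the MODEL statement cannot be seen.

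**What to change.** In 2.4.1 and 2.4.2, delete patient and patient by time from the fixed effects. Suggested wording: *Fixed effects: administration group, time (years) and administration group × time. Random effects: intercept and slope over time by patient, unstructured covariance.* Obtain the pre and post slopes, SEs and CIs by ESTIMATE statements, and keep the group × time coefficient for the slope difference. Make the prose agree with 1.4.5.2; if the code already has this form, only the prose changes.

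The cost is wording in two sections and at most one MODEL statement; no new data are needed. Group-slope CIs may widen. The model assumes that patients with one period only share the slope distribution of the others.

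A single random slope also does not cover between-patient variation in the pre-to-post slope change. With an assumed SD of 0.012 in that change, coverage of the slope difference is about 94% (A) or 91–93% (B), much as for the model as worded (94% and 92%), and pre-slope coverage can fall to 90.5% (B). Nominal coverage is therefore not assured if that variation is large.
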